### 10.2.1 Analyses of Secondary Endpoints

Secondary Outcomes will be analyzed as described in Section 10 for the eight survey assessment measures detailed in Section 6.4.2.

The Change in Affective Reactivity to Stress as Measured by the Daily Modified Differential Emotions Scale (mDES) measure and the Change in Affective Reactivity to Stress as Measured by the Daily Inventory of Stressful Events (DISE) will be analyzed using mixed-effects analysis of variance with treatment group by time (Baseline, Post-Intervention, 1-Month Follow-Up) by day in burst (1, 2, ..., 7). Models will include fixed (linear) effects for treatment (LARKSPUR vs. control), time (Baseline, Post-Intervention, 1-month Follow-Up), day in burst, and the interactions between treatment group, time, and day in burst. Random intercepts for participants and random slopes for linear day in burst effects will be included to account for within-participant correlation over time. The modified Intention-to-Treat sample described in Section 8.1 will be used. Treatment groups will be compared at Post-Intervention, at 1-Month Follow-Up, and with respect to their change from Post-Intervention to 1-Month Follow-Up using 2-sided tests at the 5% significance level under the null hypothesis of no difference in means/change. All assumptions for the mixed-effects models will be assessed by inspection of plots of within-participant and between-person residuals. Standard errors, degrees of freedom, 95% confidence intervals, and p-values will be adjusted using the Kenward-Roger method to control the significance level [4]. Restricted maximum likelihood (REML) estimation will be used. All analyses are exploratory with the aim of hypothesis generation as described in the Study Protocol given the pilot nature of this study.

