### **5.2.2 Secondary Endpoints**

**5.2.2.1** Change in FMS Pain as Measured by PROMIS Pain Intensity – Short Form 3a

**5.2.2.2** Change in FMS Pain as Measured by PROMIS Pain Interference – Short Form 6b

**5.2.2.3** Change in Depressive Symptoms as Measured by the Center for Epidemiologic Studies Depression Scale Revised (CESD-R-10)

**5.2.2.4** Change in Positive Affect as Measured by the Modified Differential Emotions Scale (mDES)

**5.2.2.5** Change in Positive Affect as Measured by the Positive and Negative Affect Scale (PANAS-GEN)

**5.2.2.6** Change in Physical Functioning as Measured by PROMIS Physical Functioning Short Form 10a

**5.2.2.7** Change in Physical Functioning as Measured by PROMIS Fatigue – Short Form 6a

**5.2.2.8** Change in Stress Appraisal as Measured by the Perceived Stress Scale

**5.2.2.9** Change in Affective Reactivity to Stress as Measured by the Daily Modified Differential Emotions Scale (mDES)

**5.2.2.10** Change in Affective Reactivity to Stress as Measured by the Daily Inventory of Stressful Events (DISE)

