##### **6.4.2.6.1 Change in Affective Reactivity to Stress as Measured by the Daily Modified Differential Emotions Scale (mDES)**

A 20-item instrument that measures the extent to which a patient has experienced positive and negative emotions over a chosen time frame; in the version used in this survey, we ask for emotions over the past 24 hours [11]. Respondents are asked to report the greatest amount of a given emotion on a five-point scale: 0=Not at all, 1=A little bit, 2=Moderately, 3=Quite a bit, 4=Extremely. mDES mean scores range from 0 (not at all experienced positive emotion) to 4 (extremely positive emotion).

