**6.4.2.6.2      *Change in Affective Reactivity to Stress as Measured by the Daily Inventory of Stressful Events (DISE)***

A 7-item self-report instrument in which participants report whether stressful events have occurred within the past 24 hours, indicating 1=yes or 0=no accordingly [13].

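### The two endpoints named affective reactivity to stress are modelled without a stressor term, so they estimate mean daily affect and stressor reporting instead

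*SAP*

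**What the plan says.** SAP 5.2.2 lists ten secondary endpoints. The ninth is "Change in Affective Reactivity to Stress as Measured by the Daily Modified Differential Emotions Scale (mDES"). The tenth has the same construct name, with the DISE as its instrument.

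SAP 6.4.2.6 describes the two instruments, each completed over a 7-day burst at the three assessments. For the 24-hour mDES, "mDES mean scores range from 0 (not at all experienced positive emotion) to 4 (extremely positive emotion"). For the seven-item DISE, "participants report whether stressful events have occurred within the past 24 hours, indicating 1=yes or 0=no". Neither subsection combines the instruments or derives a reactivity score.

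SAP 10.2.1 gives both measures the same model, a "mixed-effects analysis of variance with treatment group by time (Baseline, Post-Intervention, 1-Month Follow-Up) by day in burst". The fixed effects are treatment, time, "day in burst, and the interactions between treatment group, time, and day in burst". On the random part it says: "Random intercepts for participants and random slopes for linear day in burst effects will be included to account for within-participant correlation over time". On the comparisons: "Treatment groups will be compared at Post-Intervention, at 1-Month Follow-Up, and with respect to their change from Post-Intervention to 1-Month Follow-Up", against a null of equal means or equal change. It adds: "All analyses are exploratory with the aim of hypothesis generation".

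SAP 6.1 puts every secondary endpoint under a superiority test. SAP section 10 exempts these two measures from the general model and says nothing about a stressor term. Protocol section 8 does not mention reactivity.

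**The concern.** The documents do not define affective reactivity. Read naturally, it is how far a person's affect differs between days with and without a stressor. Estimating it requires affect as the outcome and stressor exposure as a predictor in the same model. The SAP keeps them apart: the DISE never enters the mDES model, and the DISE as described has no affect item.

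The SAP itself treats positive affect (5.2.2.4, mDES with 7-day recall) and reactivity (5.2.2.9, daily mDES) as different endpoints. Without a stressor term, the second is the first with a 24-hour recall.

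What is at stake is the construct reported. SAP 5.1.2 hypothesises more frequent daily positive affect. If that happens and reactivity is unchanged, the planned test would tend to favour LARKSPUR and the result would be reported as changed stress reactivity. A pilot meant to prepare a larger trial would then pass on a wrong signal about mechanism. Conversely, a real change in reactivity would be diluted.

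**Working it through.** The SAP states no figure for these endpoints, so there is nothing to reproduce. The check is of what each contrast estimates.

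**Estimand.** At one assessment, let arm *g* (L = LARKSPUR, C = control) have mean affect a_g on non-stressor days, stressor slope β_g (negative) and stressor-day proportion p_g.

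- Planned mDES contrast: (a_L + β_L p_L) − (a_C + β_C p_C)
- Planned DISE contrast, if scored as any stressor: p_L − p_C
- Reactivity contrast: β_L − β_C

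The first mixes level, slope and exposure. The second contains no affect.

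**Illustration.** All values are assumptions, with control slope −0.5.

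| What LARKSPUR changes | Planned mDES contrast | Reactivity contrast |
|---|---|---|
| Slope to −0.3, p = 0.2 / 0.4 / 0.6 | 0.20 × p = 0.04 / 0.08 / 0.12 | 0.20 |
| Slope to −0.25, non-stressor days 0.10 lower, p = 0.4 | 0.25 × 0.4 − 0.10 = 0.00 | 0.25 |
| Uniform mood shift of 0.20 | 0.20 | 0 |
| Stressor days from 40% to 30% | −0.5 × (0.3 − 0.4) = 0.05 | 0 |

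A simulation with 200,000 people per arm agreed: planned contrasts 0.039 / 0.076 / 0.120, −0.003, 0.202 and 0.051; slope contrasts 0.203 / 0.200 / 0.199, 0.250, 0.004 and 0.000.

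A separate check fitted the mixed models at 45 per arm (40 replicates, slope −0.4, p = 0.4). With reactivity halved at equal mean affect, the planned mDES contrast averaged 0.03 (true 0), and a treatment × time × stressor term averaged 0.21 (true 0.20). With stressor days cut from 40% to 20% and reactivity unchanged, the planned contrasts were 0.08 (mDES) and −0.20 (DISE), and the stressor term −0.01.

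**Precision of a reactivity contrast.** For a pooled slope centred within each burst, with m completed days, n per arm and daily SD σ:

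SE = σ √[2 / (n (m − 1) p(1 − p))]

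Take σ = 0.67 (assumed) and a true difference of 0.20. The half-width is 1.96 × SE and power is Φ(0.20/SE − 1.96). Each range runs from p = 0.4 or 0.6 (smaller SE) to p = 0.2 (larger SE).

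| n per arm, days | SE | 95% half-width | Power |
|---|---|---|---|
| 45 (SAP section 7), 7 | 0.118–0.144 | 0.23–0.28 | 40–28% |
| 45, 5 | 0.144–0.177 | 0.28–0.35 | 28–20% |
| 75 (Protocol section 3), 7 | 0.091–0.112 | 0.18–0.22 | 59–43% |

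Simulated SEs were within 0.002 of these. If slopes vary between people with SD 0.2, the SE at 45 per arm and 7 days is 0.125–0.151 (power 36–26%).

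**Secondary caution: burst variance.** This is conditional and held with less confidence. The random effects have no participant-by-burst intercept. Suppose the true variances, as shares of the total, are σ_e² = 0.45 (daily residual) and σ_b² (burst), with 7 complete days in each of three bursts.

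- The planned model's residual becomes σ_e² + (14/20) σ_b².
- With h(d) = 1/7 + (d − 4)²/28, the true-to-model variance ratio for the Post-Intervention to 1-month change at day d is [σ_b² + σ_e² h(d)] / {[σ_e² + 0.7 σ_b²] h(d)}.
- Example, σ_b² = 0.05 at day 4: (0.05 + 0.0643)/(0.485/7) = 1.65, SE ratio 1.284, and type I error 2Φ(−1.96/1.284) = 12.7%.

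| Comparison day | σ_b² = 2% | 5% | 10% |
|---|---|---|---|
| 4 (the 7-day average) | 8.2% | 12.7% | 18.8% |
| 1 or 7 | 5.7% | 6.8% | 8.3% |
| 0 (uncentred day) | 5.3% | 5.8% | 6.6% |

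At Post-Intervention or 1 month alone, the error stays between 5.0% and 6.3%. With zero burst variance it is 5.0% throughout. SAP 10.2.1 includes day in the interactions but does not say at which day the arms are compared.

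**The case against.** The strongest reply is that this is mainly a labelling fault with limited reach. The analyses are declared exploratory, SAP 4.2 says the trial is not powered for outcome differences, and the objectives in SAP 5.1.1 do not list reactivity. SAP 6.1 justifies superiority testing with a hypothesis list that also omits it. The instrument descriptions state openly what is measured. If the mDES score is the positive-emotion mean, its model does answer the stated hypothesis about daily positive affect. All of this stands as a limit on consequence. It does not make either contrast estimate reactivity, since exploratory status relaxes error control and not the meaning of an estimate.

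The construct is also not defined in the documents. That is true, but the DISE result does not depend on the definition: a model with no affect in it cannot estimate affective reactivity.

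The slope model would be imprecise. That stands too. The figure of 45 per arm is a recruitment target. At the roughly 80% retention the Protocol reports from earlier work (36 per arm), the formula gives half-widths of about 0.26 to 0.32 and power of 33% down to 24%. This favours renaming as the practical remedy.

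The scenario in which a reactivity change cancels completely needs affect on non-stressor days to fall, against the hypothesised direction; dilution is the ordinary case. The burst figures rest on unknown variances and on the comparison day, so they show sensitivity and not a demonstrated error rate.

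**Conclusion.** The concern holds and should be fixed. Followed exactly, SAP 10.2.1 would report mean daily affect and stressor reporting under the name of affective reactivity, and no other section repairs this. The conclusion rests on the text and simple algebra.

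Only the sizes rest on assumptions: a 0.20 weakening of the stressor slope would appear as 0.04 to 0.12, while a 0.20 mood shift with no change in reactivity would appear in full. The burst-intercept point is a conditional, secondary caution that matters mainly for the Post-Intervention to 1-month change. Feasibility, acceptability and the eight survey outcomes are unaffected.

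**What to change.** **Minimum.** Rename the two endpoints as daily positive affect (the 24-hour mDES positive-emotion mean) and daily stressor exposure. State how the seven DISE items are summarised, as any stressor or as a count. This is wording only.

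**If a reactivity endpoint is kept.** Define it as the within-person difference in daily mDES score between stressor and non-stressor days. State whether positive or negative items are scored and what counts as a stressor day. Model daily mDES with the stressor-day indicator centred on the participant's mean in that burst, that mean as a separate term, and treatment × time × stressor. Report the arm difference in stressor slope at Post-Intervention and at 1 month as an estimate with its interval, and name a simpler fallback model. The daily stressor and affect items are already collected (SAP 6.4, Table 1). The cost is an imprecise estimate at 45 per arm.

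**Separately.** State the day in burst at which arms are compared, for example the 7-day average; this is wording only. Add a participant-by-burst random intercept with a rule for non-convergence. If burst variance is present, this widens the interval for the Post-Intervention to 1-month change.

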- Week 4: Positive Reappraisal and Gratitude
- Week 5: Acts of Kindness
- Week 6: Wrap-Up

The following table is the LARKSPUR intervention content.

Table 1. Intervention Content

Week 1	Noticing and Savoring Positive Events	Recognizing cognitive biases that can lead to discounting or failing to remember positive events. Skills for scheduling pleasant events according to level of pain
	Exercises	Daily positive events journal
Week 2	Strengths and Activation	Support for acknowledging strengths even in the presence of pain-related limitations. Emphasis on setting small, attainable goals and working up to challenging goals gradually. How to select goals that will provide pleasure or mastery experiences.
	Exercises	Daily strengths journal (record ways a personal strength or talent was used) Activity journal
Week 3	Mindfulness	Using present-focused awareness to combat rumination about chronicity of pain and pain-related limitations Using acceptance to tolerate unpleasant situations with less negative emotion
	Exercises	Select an everyday activity to do mindfully Mindful breathing recorded meditation (10 minutes)
Week 4	Positive Reappraisal and Gratitude	Role of negative cognitions in causing or maintaining stress and contributing to pain
	Exercises	Daily reappraisal journal Daily gratitude journal
Week 5	Acts of Kindness	Include benefits of compassion toward self and others (e.g., decreased stress and pain; improved relationships) Small prosocial acts that can be performed even if one is relatively socially isolated or has limited mobility
	Exercises	Do something nice for someone else each day and record it in a daily kindness journal
Week 6	Wrap-Up	Review the LARKSPUR course, reflect on skills learned, and make a plan for continued practice.

Randomization. Once participants complete consent and baseline questionnaire, participants will be randomized 1:1 to LARKSPUR (n = 75) or an emotion reporting only attention control condition (n = 75) stratified by race/ethnicity. The random number sequence will be generated and uploaded into REDCap by a non-data collecting co-investigator under the guidance of the study statistician and REDCap/CTSC personnel. All participants will know their intervention/attention control status.

LARKSPUR intervention (n = 75). The LARKSPUR intervention will be based on our current online positive affect intervention which consists of skills for increasing the frequency of positive emotions, beginning

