#### **6.4.2.6 Daily Survey Assessments**

Assessed over 7-day periods at Baseline, Post-Intervention, and 1-Month Follow-Up.

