**7      Sample Size**

Given that the primary purpose of this study is to assess the feasibility of methods and procedures to be used in a larger, fully powered trial of LARKSPUR, sample size was chosen based on feasibility indicators (recruitment, retention, adherence) rather than on formal power calculations, as appropriate for the pilot nature of the study [see 1]. For quantitative pilot studies, sample sizes of 30 per treatment arm have been proposed to establish feasibility [2]. To allow for attrition between end-of-trial and follow-up, we aimed to recruit 45 per group (intervention and control). Findings from subgroup analyses should therefore be interpreted with caution and call for further confirmatory randomized trials [3].

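### The daily-survey model in SAP 10.2.1 has no participant-by-burst random effect, so its test of arm difference in change from Post-Intervention to 1-Month exceeds 5% if participants shift between bursts by differing amounts

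*SAP*

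**What the plan says.** SAP 6.4.2.6 sets the schedule for the daily mDES and the DISE: "Assessed over 7-day periods at Baseline, Post-Intervention, and 1-Month Follow-Up". Each participant can therefore contribute 3 × 7 = 21 daily records, the total that Protocol Section 3 also gives.

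SAP 10.2.1 models these records with fixed effects for treatment, time (three levels), "day in burst, and the interactions between treatment group, time, and day in burst". On the covariance it says only: "Random intercepts for participants and random slopes for linear day in burst effects will be included to account for within-participant correlation over time". It names no participant-by-time term and no residual serial correlation.

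The arms are to be compared at Post-Intervention, at 1-Month Follow-Up, and "with respect to their change from Post-Intervention to 1-Month Follow-Up", in each case "using 2-sided tests at the 5% significance level under the null hypothesis of no difference in means/change". Standard errors, degrees of freedom, intervals and p-values are to be "adjusted using the Kenward-Roger method to control the significance level". Residual plots are planned, but no action is attached to them. The section describes all its analyses as exploratory.

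**The concern.** The data have three levels: days within bursts, and bursts within participants. The bursts are separated by the 6–8-week intervention period and then by about a month. I read the plan as one intercept and one day slope per participant, both shared by all three bursts. Nothing then allows a participant's whole week to lie above or below that person's usual level after the group mean shift is removed.

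If such week-level shifts exist, all seven days of a burst share them. The model puts the shift into the day-level residual and averages it over seven days as if they were independent. A change between bursts is the comparison where this matters most. Kenward-Roger does not help: it corrects small-sample inference under the covariance that is specified, and cannot supply a variance component that was left out.

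At stake are the p-value and 95% interval for the arm difference in change from Post-Intervention to 1-Month on the daily endpoints. That result bears on whether an effect persists, in a pilot meant to inform a larger trial.

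**Working it through.** **Inputs from the documents.** 7 days per burst and 3 bursts (SAP 6.4.2.6). Two-sided 5% (SAP 10.2.1). Per arm: 45 (SAP Section 7), 75 (Protocol Section 3, Randomization), and 30 as the pilot benchmark cited in SAP Section 7.

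**Assumptions.** q = σ_b²/σ_e², the participant-by-burst variance over the day-level variance, is in neither document; the range 0 to 0.50 is assumed. The score is continuous, and the contrast is taken at the average day (day 4).

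**Step 1: true variance.** For participant i, burst j, day k, write the score as fixed effects + u_i + v_i·day + b_ij + e_ijk. In the difference between two burst means, u_i cancels, and so does v_i because each burst covers days 1–7. What remains has variance 2(σ_b² + σ_e²/7).

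**Step 2: variance the planned model uses.** Without b_ij the model uses 2s/7, where s is its residual variance. A participant has 21 records, less one intercept and one slope, leaving 19 degrees of freedom. Burst shifts add 7 × (3 − 1)σ_b² = 14σ_b² to the residual sum of squares, so s = σ_e² + (14/19)σ_b².

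**Step 3: ratio and size.** R = (1 + 7q)/(1 + 14q/19), and size = 2[1 − Φ(1.96/√R)].

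At q = 0, R = 1 and the plan's 5% is reproduced. At q = 0.10, R = 1.70/1.0737 = 1.583, √R = 1.258, 1.96/1.258 = 1.558, and the size is 11.9%.

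The closed form was checked by simulating null trials (balanced data, REML, 3,000 trials per setting):

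| q | R | SE too small by factor √R | Size, closed form | Simulated, 30/arm | 45/arm | 75/arm | 45/arm with burst intercept added |
|---|---|---|---|---|---|---|---|
| 0 | 1.000 | 1.00 | 5.0% | 5.1% | 5.1% | 4.9% | 4.9% |
| 0.02 | 1.123 | 1.06 | 6.4% | 6.7% | 6.8% | 6.0% | 5.5% |
| 0.05 | 1.302 | 1.14 | 8.6% | 8.6% | 9.2% | 8.3% | 5.3% |
| 0.10 | 1.583 | 1.26 | 11.9% | 11.6% | 11.0% | 12.6% | 3.9% |
| 0.25 | 2.322 | 1.52 | 19.8% | 19.0% | 19.9% | 19.0% | 4.8% |
| 0.50 | 3.288 | 1.81 | 28.0% | 29.3% | 27.1% | 27.6% | 5.1% |

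The number per arm makes no material difference, so neither 45 nor 75 cures the problem. Over all three sample sizes, the model with the burst intercept gave 3.9–5.7%.

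**Step 4: further checks.**

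- *Missing data.* Mixed models with Wald tests (no Kenward-Roger), 30 per arm, 20% without the 1-Month burst, 15% of days missed, 300 trials per setting. As written: 6.3%, 11.0% and 15.0% at q = 0, 0.10 and 0.25. With the burst intercept: 3.7%, 7.0% and 6.3%. The Monte Carlo error is about 1 to 2 points.
- *Serial correlation instead of burst variance.* With q = 0 and AR(1) correlation between days of 0.1, 0.2, 0.3 or 0.5, the size as written is 7.6%, 10.9%, 14.0% or 23.2%.
- *Contrast at an uncentred day 0.* The estimate is then extrapolated, and 1/7 is replaced by 1/7 + 4²/28 = 5/7. R becomes (1 + 7q/5)/(1 + 14q/19). At q = 0.50 this is 1.70/1.368 = 1.242, which gives 7.9%. Simulation gave about 5–8% over the whole range of q.
- *Arms compared at Post-Intervention alone.* About 5–8% in the balanced simulation over the same range, because the participant intercept, which is in the model, carries most of that variance.

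**The case against.** The strongest reply is that little depends on this test. It is one of three contrasts on two of the ten secondary endpoints in SAP 5.2.2. The stated hypotheses concern differences immediately after the intervention and at one month, which are single-time comparisons and only mildly inflated. The primary endpoints are not analysed with this model. The eight survey measures, including both pain scales, have one score per time point and use the Section 10 model, which does not share the problem. SAP 8.4 gives study-wide error control less weight, and 10.2.1 calls the analyses exploratory. All of this stands, and it lowers the severity. It does not make the stated 5% level or the intervals correct, and SAP 8.4 itself relies on confidence intervals to convey uncertainty.

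Second, the size is unknown. A reader might infer that the test is bound to reject well above 5%. The documents do not support that: they give neither a between-burst variance nor a day-to-day correlation. At q = 0.02 the size is 6.4%, and a marked excess needs q of roughly 0.05–0.10 or more, or comparable serial correlation. On the other side, q = 0 requires every participant's true level to move between bursts by exactly the group mean.

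Third, 10.2.1 does not say how day is coded, and at an uncentred day 0 the inflation is slight. Its null hypothesis refers to means and change, which favours the average-day reading, but the plan should say so.

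Fourth, the DISE consists of seven yes/no items. The calculation is for a continuous score, and none was made for the DISE.

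Finally, a reader might infer that a planned Baseline to Post-Intervention test is inflated too. That contrast would behave in the same way, but 10.2.1 does not list it.

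**Conclusion.** The concern holds as a conditional specification gap. The structural part is exact under the reading of one intercept and one slope per participant: both cancel from the Post-Intervention to 1-Month change, so the planned standard error counts seven days of a burst as independent. Unless between-burst variance and within-burst serial correlation are both nil, the 5% level and the 95% intervals for that contrast do not hold.

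The amount rests on an assumed q: from no effect at q = 0, through 8.6% at 0.05 and 12% at 0.10, to 28% at 0.50, with standard errors too small by a factor of 1.00 to 1.81. These figures apply to a continuous score at the average day. Whether the DISE is affected to the same extent was not calculated.

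Severity is moderate. A reader might infer that the trial's main results are unreliable or that the analysis cannot proceed without this change. The documents do not support that, because only an exploratory contrast on secondary endpoints is materially exposed.

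**What to change.** In SAP 10.2.1:

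1. Add a random intercept for participant-by-time (burst), so that days are nested in bursts and bursts in participants. Keep REML and Kenward-Roger.
2. Centre day in burst, and state that all treatment contrasts refer to the average day.
3. Name a fallback for non-convergence: analyse each participant's burst mean with the Section 10 model.

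The cost is a few sentences and one more variance parameter. Intervals for the daily change contrast will be wider if burst variance is present. If it is absent, little is lost: with the added term the simulated size at q = 0 was 4.9% at 45 per arm.

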**8      General Analysis Considerations****8.1    Analysis Populations****8.1.1    Modified Intention to Treat Population**

All subjects who received any study drug and who participated in at least one post-baseline assessment (i.e., all randomized participants with data following the treatment intervention window).

Participants may be removed from the Modified Intention to Treat Population for analysis if they have (a) no observed data on Post-Intervention assessments, (b) withdrew consent during the study, or (c) were unable to access the online intervention and daily emotion reporting platform.

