### **8.3 Missing Data**

All missing data due to early discontinuation of participants from the study or otherwise will be handled using mixed-effects modeling (i.e., multilevel modeling) with participant random intercepts. Multilevel models yield unbiased and consistent estimates of model parameters of interest in the presence of missing outcomes under either Missing Completely at Random or Missing at Random missing data mechanisms. Sensitivity to this assumption will be assessed by comparing analytic results using the modified intention to treat sample to complete-case analyses. Complete-case analyses yield unbiased and consistent estimates under a Missing Completely at Random missing data mechanism, although they are less efficient due to the removal of participant data.

Study personnel will make concerted efforts to follow-up with participants that prematurely discontinue participation in the study to understand potential reasons for their discontinuation where possible.

Participant retention and attrition will be summarized at each primary assessment point in the study (Baseline, Post-Intervention, and 1-Month Follow-Up).

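### The daily-survey models treat Baseline as an outcome but drop participants who have only Baseline data, so the Missing-at-Random claim in SAP 8.3 fails for the Post-Intervention and 1-Month arm contrasts

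*SAP*

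**What the plan says.** SAP 10.2.1 analyses daily mDES and DISE by "mixed-effects analysis of variance with treatment group by time (Baseline, Post-Intervention, 1-Month Follow-Up) by day in burst". SAP 6.4.2.6 gives the data structure: "Assessed over 7-day periods at Baseline, Post-Intervention, and 1-Month Follow-Up". Baseline is thus a response with up to seven observed days. The random effects are a participant intercept and a linear day slope. Arms are compared at Post-Intervention, at 1-Month Follow-Up, and on the change between the two.

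The analysis set is fixed by the sentence "The modified Intention-to-Treat sample described in Section 8.1 will be used". SAP 8.1.1 admits those who "participated in at least one post-baseline assessment (i.e., all randomized participants with data following the treatment intervention window". It also permits, but does not require, removal for condition "a) no observed data on Post-Intervention assessments".

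Two other sections bear on this. SAP 8.3 assigns missing data from early discontinuation to the mixed model and states: "Multilevel models yield unbiased and consistent estimates of model parameters of interest in the presence of missing outcomes", under Missing Completely at Random or Missing at Random. Its only sensitivity analysis compares the modified ITT sample with complete cases. SAP 8.2 says the analysis of each secondary outcome will adjust for Baseline scores. SAP 10 does this for the eight survey measures but exempts the two daily endpoints, and 10.2.1 names no Baseline covariate for them.

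**The concern.** A likelihood-based mixed model is valid under Missing at Random because partly observed participants stay in it: their observed Baseline responses correct the later arm means for who left. Here those participants are removed before fitting. Treatment by time is unrestricted, so the Post-Intervention and 1-Month contrasts become, in essence, raw differences between the people retained in each arm. If dropout depends on Baseline affect differently by arm, those differences are biased even though the data are Missing at Random.

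Such a difference is plausible here, though the documents do not establish it. LARKSPUR has lessons, daily practice and locked progression; control is a report of about five minutes a day; participants know their arm. The SAP itself tests whether retention differs between arms. If people with low positive affect left LARKSPUR more often, the retained LARKSPUR group would look better on daily positive affect without any treatment effect, and SAP 8.3 would describe that estimate as unbiased.

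**Working it through.** The plan states no figure to reproduce. The property in dispute is absence of bias under Missing at Random, so the check sets a true treatment effect of zero and lets dropout depend only on the observed Baseline burst.

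**Inputs**
- From the documents: three bursts of seven days (SAP 6.4.2.6); the model and analysis set (SAP 10.2.1, 8.1.1); past retention of about 80% for the control condition, with no time point given (protocol section 3, attention control condition), used here as 20% loss before Post-Intervention.
- Assumed, because the documents give no variances: person SD 0.7, burst SD 0.3, day SD 0.5; dropout odds ratio of 1.5 to 3 per SD lower Baseline burst mean.

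**Step 1. Correlation between bursts.** Variance of a 7-day mean = 0.7² + 0.3² + 0.5²/7 = 0.490 + 0.090 + 0.036 = 0.616, so its SD is 0.785. Correlation between two bursts = 0.490/0.616 = 0.796.

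**Step 2. Shift in Baseline among those retained.** Let z be the standardised Baseline burst mean and logit p(z) = a − ln(OR)·z, with a chosen so that average dropout is 0.20. The shift is E[z(1 − p(z))]/0.80, by numerical integration over a standard normal z.

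**Step 3. Bias in the modified ITT contrast.** Bias in SDs of the 7-day mean = 0.796 × (LARKSPUR shift − control shift).

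| Dropout odds ratio, LARKSPUR / control | Shifts | Bias (SD) |
|---|---|---|
| 1.5 / 1 | 0.079 / 0 | 0.063 |
| 2 / 1 | 0.129 / 0 | 0.103 |
| 3 / 1 | 0.186 / 0 | 0.148 |
| 2 / 1.5 | 0.129 / 0.079 | 0.040 |
| 3 / 2 | 0.186 / 0.129 | 0.045 |
| equal in both arms | equal | 0 |

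**Step 4. Keeping Baseline-only participants.** The model then subtracts its own regression slope times the shift. With the SAP's random intercept only, burst variation is partly read as person variation and the correction overshoots: large-sample simulation leaves −0.011, −0.019 and −0.028 SD for odds ratios 1.5, 2 and 3. With a participant-by-burst effect the slope is 0.796 and the residual bias is zero.

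**Step 5. Check by fitting the model.** REML fits to daily data with 45 per arm, true effect 0.30 SD, about 20% dropout, odds ratio 2 in LARKSPUR only and 150 replicates (day slope omitted) gave a mean Post-Intervention contrast of 0.43 in the modified ITT sample and 0.29 with Baseline-only participants kept. The empirical SDs were 0.23 and 0.21, so keeping them cost no precision.

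**Step 6. The SAP's random intercept and day slope, with other assumed variances** (person variance 0.60, day variance 0.40), a steeper log-odds slope of 1.2 per SD in LARKSPUR only, 20% dropout and true effect zero:
- With all randomised participants kept, bias was 0.001 SD, so the SAP 8.3 property is reproduced when its model is correct.
- In the modified ITT sample, bias was 0.18 SD, and 0.14 SD when burst-level variance of 0.15 replaced part of the person variance.
- Type I error at Post-Intervention in the modified ITT sample was 11.8% at 45 per arm and 15.0% at 75 per arm, against 4.0% and 5.5% with everyone kept (400 replicates, Wald z rather than Kenward-Roger).
- Across all scenarios run, the change from Post-Intervention to 1-Month had bias of at most 0.009 in raw units, and complete-case bias matched modified ITT bias within 0.005 SD.

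**The case against.** The strongest reply is SAP 8.2. The daily endpoints are secondary endpoints, and 8.2 promises Baseline adjustment for each one. If a Baseline covariate were in the model, the modified ITT restriction would do little harm: under the variances of step 1, Baseline-adjusted bias was within 0.002 SD. That stands as arithmetic, but it does not rescue the plan as written. The specific model in 10.2.1 uses Baseline as a response, and Section 10 exempts these endpoints from the Baseline-adjusted model. What remains is a conflict between 8.2 and 10.2.1 that has to be resolved.

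A second reply is that a change-from-Baseline contrast in the same sample would have little bias, −0.02 to −0.04 SD at 20% dropout. That is true, but 10.2.1 does not test that contrast.

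Third, a reader might infer 33% early dropout from SAP 7 (45 recruited, 30 needed) and arrive at a larger bias. The documents do not support this. SAP 7 ties the allowance to attrition after end of trial, and people lost then can have Post-Intervention data and remain in the sample.

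Fourth, these analyses are labelled exploratory, and the bias is small beside the 0.23 SD spread of the estimate in step 5. This lowers the consequence. It does not restore the claim in 8.3.

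**Conclusion.** The concern holds for the Post-Intervention and 1-Month contrasts of the two daily endpoints. The Missing-at-Random guarantee is lost; bias is possible, not certain. It needs Baseline-related dropout that differs between arms in rate, strength or direction, and is zero if the pattern is the same in both. At 20% dropout the size is about 0.04 SD with dependence of different strength in both arms, and 0.06 to 0.15 SD with dependence in LARKSPUR only. These figures rest on assumed variances and dropout odds ratios, so direction and order of magnitude are what to rely on. The calculations are Gaussian; DISE, with seven yes/no items, was not simulated, although the same deletion of data applies to it.

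A reader might also infer that all three arm contrasts, or the Aim 2 effect size as a whole, are inflated. Neither follows. The change from Post-Intervention to 1-Month is essentially unaffected. Pain and the other main Aim 2 outcomes are survey measures whose models condition on Baseline, so participants with only Baseline data would add nothing to them.

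The planned sensitivity analysis offers no protection, because both of its samples omit early dropouts.

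**What to change.** In SAP 10.2.1, for the two daily endpoints, replace the modified ITT sentence with: *The model will be fitted to all randomised participants with at least one daily survey at any burst for whom data use is permitted, including those with Baseline data only, analysed as randomised, with a participant-by-burst random effect added.* Keep the modified ITT fit as a supplementary analysis; unlike the complete-case comparison, the contrast between the two fits can reveal this problem. In SAP 8.2, state that Baseline enters these two models as an outcome occasion rather than as a covariate. If the sponsor prefers to keep the present analysis set and model, the Missing-at-Random statement in 8.3 should be withdrawn for these endpoints.

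The cost is a few sentences and one further model run per endpoint, with no new data. The downsides are a different analysis N from the survey endpoints, which a table footnote can state, and one more variance component to estimate.
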